1.3.2. Selection and Timing of Doses

Phase 1: A single-patient dose escalation schema will be followed until the observation of \geq Grade 2 toxicity. One patient per cohort will be dosed and followed for 28 days through Cycle 1 for DLT. If no \geq Grade 2 toxicity is seen, the next patient will be enrolled at the next dose level. Dose escalation will proceed in this manner until Grade 2 or greater toxicity is observed in at least one patient per cohort during the first 28 days. At that point, the current dose cohort will be expanded to 3 patients before proceeding in standard 3+3 manner. The dose escalation in subsequent cohorts will proceed in standard 3+3 manner. For all patient cohorts, if 1 of 3 patients per cohort experiences DLT, the cohort will be expanded to 6. If 2 or more of 6 patients per cohort experience DLT, all further dose escalation will stop. If the next lowest dose has only 3 patients, 3 more patients will be treated at that dose to verify it as the MTD. If that dose turns out to be too toxic, then this process will be repeated until the MTD is found through dose de-escalation. If 0 of 3 or ≤ 1 of 6 patients per cohort experience DLT by Day 28 following dosing of FF-10502-01, dose escalation will proceed to the next cohort. The highest dose level below the dose level eliciting DLT in ≥ 2 patients will be declared the MTD. A total of 6 patients will be treated at the MTD. The MTD will be declared the RP2D. No intra-patient dose escalation will be allowed from previous dose levels until at least one patient has completed Cycle 1 at the higher dose level, with no Grade 2 or greater toxicities observed.

Dose level adjustments for DLT will be made. Patients who experience DLT at the first dose level, 8 mg/m², will not be dose-reduced, and will be discontinued.

Phase 2a: Patients in Cohorts 1 to 12 will receive FF-10502-01 on a weekly schedule for 3 weeks (Days 1, 8, and 15), repeated every 28 days. The Phase 2a dose regimen is FF-10502-01 90 mg/m², administered on Days 1, 8, and 15 of a 28-day cycle. Patients in Cohort 13 (urothelial carcinoma) will receive FF-10502-01 on a weekly schedule for 2 weeks (Days 1 and 8), repeated every 21 days.

Blood for hematology, coagulation parameters and serum chemistry determinations for Cohorts 1 to 12 will be collected within 28 days of Cycle 1 Day 1, on Days 1, 8, 15 and 22 of Cycle 1, on Day 1 of each subsequent cycle and at the End of Study Visit. Blood for hematology and coagulation parameters will be collected pre-dose on Days 8 and 15 of each cycle. Urine will be collected for urinalysis within 28 days of Cycle 1 Day 1, on Day 1 of each subsequent cycle and at the End of Study Visit. Blood for hematology and serum chemistry determinations for Cohort 13 will be collected within 28 days before Cycle 1 Day 1, on Days 1, 8, and 15 of Cycle 1, on Day 1 of each subsequent cycle, and at End of Treatment. After Cycle 1, blood for hematology also will be collected pre-dose on Day 8 of each cycle. Urine will be collected for urinalysis within 28 days before Cycle 1 Day 1, on Day 1 of each cycle, and at the End-of-Treatment Visit.

Disease assessments, based on computed tomography (CT) or magnetic resonance image (MRI) will be obtained at Week 8 and every 8 weeks thereafter until documented progression of disease (PD) for Cohorts 1 to 12; and at Week 6 and every 6 weeks thereafter until

documented PD for Cohort 13. Patients who demonstrate clinical benefit will be allowed to continue therapy with FF-10502-01 until progression of disease, observation of unacceptable AEs, intercurrent illness or changes in the patient's condition that prevents further study participation.

1.4. Procedures

1.4.1. Patient Identification

Once study eligibility has been determined, a patient will be enrolled into the study and will be assigned a sequential Patient Identification number within each participating site. The identification number will consist of a 1-digit site number, a 2-digit cohort number, and a 2 digit Patient number. The Patient identification number will be assigned sequentially within the cohort. The cohort number will remain the same if a patient's dose is increased or decreased. If a patient is replaced, the identification number will not be reassigned.

1.4.2. Randomization

Not Applicable

1.4.3. Blinding/Unblinding

This is an unblinded study.

1.4.4. Replacement

Patients who are screened, but do not receive FF-10502-01, will be replaced.

1.4.5. Data Monitoring

During the study, an SRC consisting of the actively recruiting investigators, the Medical Monitor, and FUJIFILM Pharmaceuticals (FPHU), will review data from each cohort on an ongoing basis.

The sponsor is responsible for ensuring the proper conduct of the study with regard to ethics, protocol adherence, site procedures, integrity of the data, and applicable laws and/or regulations. At regular intervals during the study and following completion of the study, the sponsor's study monitors will contact the study site via visits to the site, telephone calls, and letters in order to review study progress, CRF completion, and address any concerns or questions regarding the study conduct. During monitoring visits, the following aspects of study conduct will be carefully reviewed: informed consent of patients, patient recruitment, and patient compliance with the study procedures, source data verification, drug accountability, use of concomitant therapy by patients, AE and SAE documentation and reporting, and quality of data. Records pertaining to these aspects are expected to be kept current.

2. Statistical Analysis Considerations

2.1. Sample Size and Power

A total of up to N=161 patients with advanced solid tumors are planned in this study.

Phase 1: The sample size reflects requirements associated with a single patient dose escalation until \geq Grade 2 toxicity is observed, thereafter a 3+3 design. A total of 3 to 54 patients are planned (1 to 6 patients in each of 9 dose cohorts).

Phase 2a: The sample size reflects four additional cohorts: Cohort 10 (advanced solid tumors) will enroll up to 20 patients, Cohort 11 (cholangiocarcinoma) will enroll up to 50 patients, Cohort 12 (gallbladder carcinoma) will enroll up to 10 patients, and Cohort 13 (urothelial carcinoma) will enroll up to 27 patients for a total of up to 107 patients.

2.2. Analysis Populations

2.2.1. Full Analysis Set (FAS) Population

The FAS includes all patients who have a valid baseline and one or more post-treatment assessments. All efficacy endpoints will be based on the FAS population.

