11 STATISTICAL METHODOLOGY

11.1 Determination of Sample Size

Phase 1:

The sample size reflects requirements associated with a single patient dose escalation until \geq Grade 2 toxicity is observed, thereafter a 3+3 design. A total of 3 to 54 patients are planned (1 to 6 patients in each of 9 dose cohorts).

Phase 2a:

There are 4 cohorts in Phase 2a. The expansion cohorts will assess the efficacy of FF-10502-01 in a cohort of patients with a variety of solid tumors (Cohort 10), in a cohort of patients with cholangiocarcinoma (Cohort 11), in a cohort of patients with gallbladder carcinoma (Cohort 12), and in a cohort of patients with urothelial carcinoma (Cohort 13).

The primary measure of efficacy in these 4 expansion cohorts will be response according to the RECIST 1.1. criteria. A maximum of 20 patients will be accrued in Cohort 10, a maximum of 50 patients will be accrued in Cohort 11, a maximum of 10 patients will be accrued in Cohort 12, and a maximum of 27 patients will be accrued into Cohort 13.

Cohort 10: Cohort 10 will recruit patients with a variety of solid tumors to explore whether responses are seen in additional tumor types. If the overall response rate amongst these patients is 14%, there will be a less than 5% chance of failing to see a response in at least 1 patient.

Cohort 11 (cholangiocarcinoma): Historically, very low response rates have been observed in cholangiocarcinoma. Cohort 11, with a maximum of 50 patients, has 80% power if the true response rate, p_1 , is 16%, using a 1-sided type I error of 5% with a null hypothesis, p_0 , of 5%. A Simon 2-stage design will be employed so that 50 patients are only recruited if evidence of activity is confirmed at an interim analysis. If after 25 patients have been recruited, there are 1 or fewer responses, enrollment for this cohort may be suspended for futility. If after 50 patients have been recruited, 6 or more responses are observed, the null hypothesis of a 5% response rate will be rejected. An alternative analysis may include all treated cholangiocarcinoma patients—not just those meeting the definition of Cohort 11.

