11.2 Analysis Populations

The safety analysis set includes all patients who are administered any fraction of a dose of study drug. For a particular measure, the full analysis set (FAS) includes those patients who have a valid baseline and one or more post-treatment assessments for that measure of interest.

The PK population consists of all patients in the FAS who complete a baseline and at least one follow-up PK assessment.

The pharmacodynamic () population consists of all patients in the FAS who complete a baseline and at least one follow-up pharmacodynamic assessment.

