11.3.2 Efficacy Analyses

11.3.2.1 Primary Efficacy Endpoint

The primary efficacy endpoint is the proportion of patients in each disease cohort (cholangiocarcinoma, gallbladder carcinoma, urothelial carcinoma, or other solid tumor) with objective response (OR) within 4 cycles of study drug. Thus, this is the proportion of patients in Cohorts 1-12 with an OR within 16 weeks of their first dose of study drug and the proportion of patients in Cohort 13 with an OR within 12 weeks of their first dose of study drug. The OR rate is defined as the proportion of patients in the FAS with a confirmed complete or partial response. Ninety percent confidence intervals for the OR rate will be estimated.

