2.2.3. Safety Population

The safety analysis population includes all patients who are administered any fraction of a dose of study drug.

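### The response rate is reported on a full analysis set that omits treated patients with no post-baseline tumour scan, so any such omission inflates it

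*SAP*

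**What the plan says.** SAP 2.2.1 defines one FAS: "The FAS includes all patients who have a valid baseline and one or more post-treatment assessments". It does not name the kind of assessment. It adds that "All efficacy endpoints will be based on the FAS population", and SAP 3.3 repeats this.

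Protocol 11.2 defines the set differently, measure by measure: it "includes those patients who have a valid baseline and one or more post-treatment assessments for that measure of interest". Protocol 11.3.2.1 then fixes the denominator: "The OR rate is defined as the proportion of patients in the FAS with a confirmed complete or partial response". Both documents attach a 90% confidence interval to that rate.

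An all-treated set exists, but only for safety: "The safety analysis population includes all patients who are administered any fraction of a dose of study drug" (SAP 2.2.3).

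For Cohorts 1 to 12, tumour imaging "will be obtained at Week 8 and every 8 weeks thereafter until documented progression of disease" (SAP 1.3.2). Cohort 13 is scanned at Week 6 and every 6 weeks. Missing data are not imputed (SAP 2.3.2), and only patients who never receive drug are replaced (Protocol 7.3.2, SAP 1.4.4).

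The two-stage rules in Protocol 11.1 count a different group. For Cohort 11, "If after 25 patients have been recruited, there are 1 or fewer responses, enrollment for this cohort may be suspended for futility". The final rules are also stated per patients recruited: at least 6 responses in 50 (Cohort 11) and at least 4 in 27 (Cohort 13).

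**The concern.** Whether a patient enters the response denominator depends on what happens after treatment starts. Those most likely to miss the first scan are those doing worst, and Protocol 7.1 admits patients with ECOG 2 and an expected survival of only 3 months. None of them can be a confirmed responder, so removing them takes failures out of the denominator and leaves the numerator as it was. With no control arm, nothing offsets this, and the result is read against a fixed 5% rate.

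The SAP plans no formal hypothesis test (2.4.2), so the FAS-based rate and its interval are the efficacy result that it reports. That result also has a different denominator from the decision rules in the protocol, so the two can describe the same cohort differently.

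**Working it through.** **Inputs.** From Protocol 11.1, Cohort 11: first stage 25, stop at 1 or fewer responses, total 50, reject at 6 or more, p0 = 5%, p1 = 16%. Cohort 13: first stage 15, stop at 0, total 27, reject at 4 or more, p0 = 5%, p1 = 20%. Both claim 80% power and a 1-sided 5% type I error. The unscanned share d is an assumption, shown from 5% to 20%. No interval method is named; exact (Clopper-Pearson) 90% limits are used here.

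**Step 1: the plan's own figures.** P(reject) = sum, over first-stage counts x above the futility bound, of P(X1 = x) × P(X2 ≥ r - x), with X1 and X2 binomial.

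- Cohort 11: type I error 3.5%, power 80.7%.
- Cohort 13: type I error 4.3%, power 81.0%.

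The stated design reproduces in both cohorts.

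**Step 2: effect on the decision rules.** The rules count responses among patients recruited. An unscanned patient fills a place and adds no response, so already counts as a non-responder. The figures in Step 1 therefore stand. If the discretionary futility stop were ignored, type I error would be 3.8% and 4.4%, still below 5%.

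**Step 3: effect on the reported OR rate.** With R responders among N treated, the all-treated rate is R/N. The FAS rate is R/[N(1 - d)], so the ratio is 1/(1 - d).

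| d (assumed) | Factor | A true 5% rate appears as |
|---|---|---|
| 5% | 1.05 | 5.3% |
| 10% | 1.11 | 5.6% |
| 15% | 1.18 | 5.9% |
| 20% | 1.25 | 6.3% |

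At each cohort's rejection threshold:

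| Cohort | Denominator | Rate | Exact 90% CI |
|---|---|---|---|
| 11 | 50 treated | 6/50 = 12.0% | 5.4% to 22.3% |
| 11 | 45 in FAS (d = 10%) | 6/45 = 13.3% | 6.0% to 24.6% |
| 11 | 40 in FAS (d = 20%) | 6/40 = 15.0% | 6.7% to 27.5% |
| 13 | 27 treated | 4/27 = 14.8% | 5.2% to 30.8% |
| 13 | 24 in FAS (3 unscanned) | 4/24 = 16.7% | 5.9% to 34.2% |
| 13 | 22 in FAS (5 unscanned) | 4/22 = 18.2% | 6.5% to 36.9% |

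**Step 4: which reading affects which endpoint.**

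| Reading of the FAS | OR rate | PFS and OS |
|---|---|---|
| Protocol 11.2, per measure | Needs a tumour assessment; inflated by 1/(1 - d) | A death is itself follow-up for the measure; early deaths stay in |
| SAP 2.2.1, assessment means a tumour scan | Inflated by 1/(1 - d) | Unscanned early deaths are lost; biased upward |
| SAP 2.2.1, any assessment counts (e.g. Day 8 laboratory tests) | Almost no one is lost | Almost no one is lost |

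The protocol's definition alone is enough to inflate the OR rate. The PFS and OS bias needs the second reading, which conflicts with the protocol.

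**The case against.** **Early progressors mostly stay in.** Protocol 9.3 calls for imaging at progression and 10.2.4 allows extra scans, so a patient whose early progression is imaged has a post-treatment assessment. This stands: the loss is confined to patients who die, deteriorate or withdraw with no scan.

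**The SAP does not say that a scan is needed.** Read literally, a laboratory test would qualify and the problem nearly vanishes. That is fair for the SAP alone, but Protocol 11.2 ties the assessment to the measure, and for response that is tumour imaging. Leaving the choice open is itself a defect.

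**Efficacy is secondary.** The primary objective is safety and dose finding, and stopping for futility is discretionary. Best response and deaths are listed for all treated patients (SAP 3 and 4.3), so a reader could rebuild an all-treated rate. This limits the damage but does not correct the headline figure.

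**Stronger readings that the documents do not support.** A reader might infer that the type I error rises. If 50 or 27 FAS patients filled the cohorts, it would be 6.7% and 7.0% at d = 15%, but the rules count recruited patients and dosed patients are not replaced. A reader might also note that 5 responses fail the Cohort 11 rule while 5/40 has an exact lower limit of 5.06%, just above 5%. That needs 20% unscanned and an exact interval; at 5/41 the limit is 4.93%. Finally, a reader might infer that median OS is necessarily overstated. That requires early deaths to be excluded, which the protocol's per-measure definition does not do, and no median survival is given from which to size it.

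**Conclusion.** The point holds for the reported OR rate and its 90% interval. On the protocol's own definition the denominator excludes treated patients with no tumour assessment, and nothing available counts them as non-responders (SAP 2.4.5 was not in the text available). The error can only be upward, by 1/(1 - d): 1.05 to 1.25 for an assumed d of 5% to 20%. The true size cannot be computed from the documents. It is zero if every treated patient is scanned.

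The two-stage rules hold as written, with type I error of 3.5% (Cohort 11) and 4.3% (Cohort 13). For PFS and OS the bias is conditional on reading the SAP's single FAS as requiring a tumour assessment. The certain fault there is that the two documents define the set differently.

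**What to change.** 1. Analyse OR rate, PFS and OS in all patients who received any study drug, which is the existing safety population, by cohort.
2. State that a patient with no evaluable post-baseline tumour assessment is a non-responder in the OR rate.
3. State that deaths before the first scan are events for PFS and OS.
4. Keep the current FAS as a response-evaluable sensitivity analysis, labelled as such, and name tumour imaging as the qualifying assessment.
5. Align Protocol 11.2 and 11.3.2.1 with SAP 2.2.1 and 3.3.

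The two-stage rules need no change, and the OR rate would then share their denominator provided every recruited patient is dosed. The cost is wording in those four sections; no new data are needed. The reported response rate becomes slightly less favourable.

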2.2.2. Randomized Population

Since this is not a randomized study, there is no randomized population.

2.2.3. Safety Population

The safety analysis population includes all patients who are administered any fraction of a dose of study drug.

2.2.4. PK/PD population

The PK population consists of all patients in the FAS who complete all PK assessments. The PD population consists of all patients in the FAS who complete a baseline and at least one follow-up PD assessment.

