Once 6 patients are treated at the MTD in Phase 1, an additional 4 cohorts will be enrolled. Cohort 10 will enroll any patient with an advanced solid tumor who is otherwise eligible for this study (up to 20 patients). Cohort 11 will enroll patients with cholangiocarcinoma (up to 50 patients). Cohort 12 will enroll patients with carcinoma of the gallbladder (up to 10 patients). Cohort 13 will enroll patients with urothelial carcinoma (up to 27 patients).

Eligible patients enrolled in Phase 1 at the MTD may count towards the Phase 2a accrual.

Cohorts 1 to 12 (Both Phases):

Patients in Cohorts 1 to 12 will receive FF-10502-01 on a weekly schedule for 3 weeks (Days 1, 8, and 15), repeated every 28 days. The Phase 2a dose regimen is FF-10502-01 90 mg/m², administered on Days 1, 8, and 15 of a 28-day cycle.

Blood samples for PK assessment of FF-10502 plasma concentrations for patients in Cohorts 1 to 12 will be collected on Cycle 1 Days 1 and 15 pre-dose, immediately following cessation of infusion (within 15 minutes), between 1-2 hours post-infusion, and between 4-6 hours post-infusion. Incorporation of FF-10502 into cellular DNA of whole blood will be assessed as a pharmacodynamic endpoint pre-dose Cycle 1, Days 1, 8, and 15, and during the Day 22 visit.

Blood for hematology and serum chemistry determinations will be collected within 28 days before Cycle 1 Day 1, on Days 1, 8, 15 and 22 of Cycle 1, on Day 1 of each subsequent cycle and at the End of Treatment Visit. After Cycle 1, blood for hematology also will be collected pre-dose on Days 8 and 15 of each cycle. Urine will be collected for urinalysis within 28 days before Cycle 1 Day 1, on Day 1 of each cycle and at the End of Treatment Visit.

Cohort 13 (Phase 2a):

Patients in Cohort 13 (urothelial carcinoma) will receive FF-10502-01 on a weekly schedule for 2 weeks (Days 1 and 8), repeated every 21 days.

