Blood samples for PK assessment of FF-10502 plasma concentrations for patients in Cohort 13 will be collected on Cycle 1 Days 1 and 8, pre-dose, immediately following cessation of infusion (within 15 minutes), between 1-2 hours post-infusion, and between 4-6 hours post-infusion. Incorporation of FF-10502 into the cellular DNA of whole blood will be assessed as a pharmacodynamic endpoint pre-dose on Cycle 1 Days 1 and 8; and at any time during the Cycle 1 Day 15 visit. Blood for hematology and serum chemistry determinations will be collected within 28 days before Cycle 1 Day 1, on Days 1, 8, and 15 of Cycle 1, on Day 1 of each subsequent cycle, and at End of Treatment. After Cycle 1, blood for hematology also will be collected pre-dose on Day 8 of each cycle. Urine will be collected for urinalysis within 28 days before Cycle 1 Day 1, on Day 1 of each cycle, and at the End-of-Treatment Visit.

All Cohorts (Both Phases):

Disease assessments, based on computed tomography (CT) and/or magnetic resonance image (MRI), will be obtained at Week 8 and every 8 weeks thereafter until documented progression of disease (PD) for Cohorts 1 to 12; and at Week 6 and every 6 weeks thereafter until documented PD for Cohort 13. Patients who demonstrate clinical benefit will be allowed to continue therapy with FF-10502-01 until progression of disease, observation of unacceptable adverse events, intercurrent illness or changes in the patient's condition that prevents further study participation.

Safety will be assessed through the monitoring of AEs, clinical laboratory parameters (hematology, serum chemistry), vital sign measurements, and physical examinations. Adverse events will be classified according to the Medical Dictionary for Regulatory Affairs (MedDRA) and graded according to the National Cancer Institute Common Terminology Criteria for Adverse Events (NCI CTCAE) version 4.03.

Efficacy assessments for solid tumors will be made according to the Response Evaluation Criteria in Solid Tumors (RECIST v. 1.1)¹.

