11.3.3 Pharmacokinetic Endpoint Analysis

Mean plasma concentrations of FF-10502 will be determined at each time point by dose cohort for evaluation of dose-linearity. Because a limited number of plasma concentrations will be determined, full determination of routine PK parameters may not be possible. In addition to mean plasma concentrations, as the data allow, additional PK analyses will be provided (trough levels, $t_{1/2}$, T_{max} , C_{max} , AUC, etc). Population PK methods will be utilized to characterize the PK profile of FF-10502.

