APPENDIX C. FF-10502-01 Dosing Delays and Dose Modifications

Treatment may be delayed up to 14 days. If the patient has completed two cycles and, in the investigator's opinion, is receiving benefit, treatment may be delayed for longer than 14 days and then resumed following a discussion with the Medical Monitor. Patients who require the next treatment cycle to be held for more than 14 days due to ongoing toxicity from the prior cycle should have the dose reduced by 25%.

Patients who experience a toxicity requiring reduction in dose level may continue treatment at the lower dose level until disease progression or unacceptable toxicity. The dose level may be reduced twice in 25% decrements. For example, if the starting dose was 90 mg/m², then first dose reduction is 67.5 mg/m², and the 2nd dose reduction is 50 mg/m². Patients who continue to require dose modifications beyond this should be discontinued from the trial. Once the dose has been reduced it may not be escalated.

If a patient experiences myelosuppression, FF-10502-01 should be held and restarted according to Table 1.

Table 1. Dose Modification for Myelosuppression

Absolute Granulocyte Count (x 10⁶/L)		Platelet Count (x 10⁶/L)	Action
≤ 1000 (Grade 3 or 4)	Or	≤ 50,000 (Grade 3 or 4)	Dose is held until recovery to Grade 2 or better
Upon recovery to			
→1000 (Grade 2, 1 or normal)	And	>50,000 (Grade 2, 1 or normal)	Dose may be 75% or 100% of recommended dose at investigator discretion

Table 2. Dose Modifications for Non-Hematologic Toxicity

Non-Hematologic Toxicity	Modification
Grade ≥ 3 lasting ≤ 7 days	Withhold dose until ≤ Grade 1, resume next dose at 100%
Grade ≥ 3 lasting > 7 days	Withhold dose until ≤ Grade 1, resume next dose with a 25% reduction

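### SAP 2.2.4 restricts the PK population to patients with every PK sample, contradicting the protocol's baseline-plus-one rule and not fitting the planned population PK

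*SAP*

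**What the plan says.** The two documents define the same population differently.

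- SAP 2.2.4: "The PK population consists of all patients in the FAS who complete all PK assessments".
- Protocol 11.2: "The PK population consists of all patients in the FAS who complete a baseline and at least one follow-up PK assessment".

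For pharmacodynamics, the next sentence of SAP 2.2.4 keeps the protocol's rule: "The PD population consists of all patients in the FAS who complete a baseline and at least one follow-up PD assessment". Only the PK definition departs from the protocol, and no reason is given.

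Protocol 6.1 sets the sampling. In Cohorts 1 to 12, samples "will be collected on Cycle 1 Days 1 and 15 pre-dose, immediately following cessation of infusion (within 15 minutes), between 1-2 hours post-infusion", with a further sample 4 to 6 hours after the infusion. In Cohort 13 they "will be collected on Cycle 1 Days 1 and 8, pre-dose, immediately following cessation of infusion (within 15 minutes), between 1-2 hours post-infusion", again with a 4-to-6-hour sample.

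Protocol 11.3.3 accepts that the limited number of concentrations may not support a full set of PK parameters, and adds: "Population PK methods will be utilized to characterize the PK profile of FF-10502".

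SAP 1.1 defers the PK and PD analysis details to a separate plan, SAP 2.4.7 defers the results to a separate report, and SAP 3.3.3 assigns the analyses to an outside laboratory.

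**The concern.** A completers-only rule throws away usable data. Population PK can be fitted to incomplete profiles, so a patient with seven of eight concentrations carries nearly as much information as one with eight. Under the SAP wording that patient contributes nothing. SAP 2.3.2 leaves missing values missing unless otherwise specified, and no stated rule brings the patient back.

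The loss may also not be random. Three of the four samples on the second PK day are timed from an infusion. Appendix C holds dosing for Grade 3 or 4 myelosuppression ("Dose is held until recovery to Grade 2 or better") and withholds it for non-hematologic toxicity of Grade 3 or higher (for events lasting more than 7 days, "Withhold dose until ≤ Grade 1, resume next dose with a 25% reduction"). If the second PK-day infusion and its sampling do not take place, the patient cannot complete the set, so membership of the PK population may depend on early toxicity.

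PK is a secondary objective (Protocol 5.2). Protocol 6.1, 10.2.6 and 11.3.4 plan to relate exposure to DNA incorporation and clinical outcome. Those summaries would rest on a reduced and possibly selected group.

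**Working it through.** The documents give no PK sample size, sample-loss rate, dose-hold rate or exposure variability, so there is no planned figure to reproduce. The sample count comes from the documents. Every rate below is an assumption used for illustration.

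**1. Samples required.** There are 4 time points (pre-dose, end of infusion, 1–2 hours, 4–6 hours) on each of 2 days: Days 1 and 15 of Cycle 1, or Days 1 and 8 in Cohort 13. That makes 4 × 2 = 8. The SAP requires 8 of 8. The protocol minimum is 2: the baseline, for which the only scheduled draw is Day 1 pre-dose, plus any one of the other 7.

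**2. Loss from missed draws alone.** Let r be the chance that a draw is missed, independently between draws.

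- Excluded under the SAP: 1 − (1 − r)^8
- Excluded under the protocol: 1 − (1 − r)(1 − r^7), which is practically r, because the baseline draw is the only one that matters much

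| r | SAP excludes | Protocol excludes | Difference |
|---|---|---|---|
| 1% | 7.7% | 1.0% | 6.7 points |
| 3% | 21.6% | 3.0% | 18.6 points |
| 5% | 33.7% | 5.0% | 28.7 points |

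**3. Adding a missed second PK day.** Let h be the chance that the second PK-day infusion and sampling do not happen, and q = 1 − r.

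- Kept under the SAP: (1 − h) × q^8
- Kept under the protocol: q × [(1 − h)(1 − (1 − q)^7) + h(1 − (1 − q)^3)]

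For q = 0.95 and h = 0.2, the SAP keeps 0.8 × 0.663 = 53% and the protocol keeps 95%. Of the maximum 107 Phase 2a patients, that is about 57 against about 102. With h = 0 the figures are 66% and 95%, about 71 against about 102.

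**4. Possible bias if missing the second day is related to exposure.** Assume log-normal exposure with a CV of 40%, so the log-scale SD is √ln(1 + 0.4²) = 0.385. Let z be standardised log exposure and set logit P(miss second day) = a + ln(OR) × z, choosing a to give the stated overall proportion missing. The ratio of the completers' geometric mean to that of all treated patients is exp(0.385 × E[z | complete]), by numerical integration:

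| Miss second day | OR 1 per SD | OR 2 per SD | OR 3 per SD |
|---|---|---|---|
| 5% | 1.000 | 0.987 | 0.981 |
| 10% | 1.000 | 0.975 | 0.963 |
| 20% | 1.000 | 0.952 | 0.931 |
| 30% | 1.000 | 0.929 | 0.901 |

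The completers' summary is then about 1–4% too low when 5–10% miss the second day, and about 5–10% too low when 20–30% miss it. Without an association between exposure and missing the day, there is no bias.

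**The case against.** The strongest reply is that the SAP performs no PK analysis. It passes the work to a separate plan, a separate report and an outside laboratory, and the protocol synopsis likewise points to plans written by the laboratories. The only PK output listed in SAP 4.3 is a listing of blood-sample collection. The separate plan may use a different population, in which case SAP 2.2.4 would have no effect on results. This stands as a limit on the practical effect. It does not remove the conflict: SAP 2.2.4 defines the population and cites no other definition, so a separate plan must disagree with either the SAP or the protocol.

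A reader might infer three stronger things that the documents do not support.

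- *Every held dose removes the patient.* Protocol 8.4.2 and Appendix C allow treatment delays of up to 14 days. The documents do not say whether PK sampling moves with a postponed infusion. If it does, some of these patients could still complete all eight samples.
- *Holds are mostly due to myelosuppression.* Appendix C gives rules for both hematologic and non-hematologic toxicity and no frequencies. Protocol 8.4.2 also covers delays for other reasons.
- *The rule understates exposure in patients with toxicity.* Patients who fail the rule are removed; their exposure is not mismeasured. Any understatement concerns the treated group as a whole, and it requires that exposure relates to toxicity, which the documents do not quantify.

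Nor is the protocol rule free of loss: a missed Day 1 pre-dose sample still excludes the patient.

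**Conclusion.** Wrong as written. The contradiction between SAP 2.2.4 and Protocol 11.2 is explicit and certain, and the SAP's complete-case rule does not fit the planned population PK on limited samples.

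The size depends on loss rates that the documents do not give. With independent loss of 1–5% per draw, the SAP rule costs roughly 7 to 29 percentage points more of the patients than the protocol rule. Dependence of exclusion on early toxicity is plausible, but conditional on the second-day sampling not being moved to a postponed infusion. A downward bias of about 1–10% in the exposure summary is conditional again: on the assumed 40% CV, on an odds ratio of 2–3 per SD of log exposure, and on 5–30% missing the second day. It should not be read as an estimate for this trial. Whether partial profiles will in fact be dropped cannot be settled without the PK/PD analysis plan.

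This should be corrected, but it concerns a secondary objective and leaves the safety and response analyses untouched.

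**What to change.** Replace the PK sentence in SAP 2.2.4 with the Protocol 11.2 definition, which also matches the rule that the SAP already uses for its PD population. State that the population PK model uses all available concentrations from the patients in that population, including incomplete profiles. Carry the same definition into the separate PK/PD analysis plan so that all three documents agree.

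The cost is one sentence in the SAP and a matching sentence in the PK/PD plan. No new data, samples or patients are needed.
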